Open-Label Extension Phase: The open-label extension phase will comprise 12-months treatment for eligible subjects, with visits every 3 months. For each 3-month period subjects will be dispensed 12 tubes per month (36 tubes at each visit) to allow them to use the tubes as they require. Male subjects will be asked to complete the SEP questionnaire to record their experiences after each sexual intercourse attempt as and when they occur. At each site visit male subjects will be asked to complete the IIEF questionnaire to cover the previous 1 month. Subjects and their female partners will be monitored for AEs by completing diaries of untoward signs and symptoms as they experience them (i.e. in real time) throughout the duration of the open-label extension phase.

Once they have entered the open-term extension phase, male subjects will be asked to return to the study site every 3 months (at Day 180 [Visit 7], Day 270 [Visit 8], Day 360 [Visit 9] and Day 450 [Visit 10]) to enable the clinical staff to check AEs and concomitant medications (in the diaries), SEP questionnaire completed after each intercourse attempt to cover each 3-month period, IIEF to cover previous 1-month period and compliance on IMP usage. Vital signs and a penis examination will be undertaken at each 90 day visit. An electrocardiogram (ECG) will be done at 12 months (Day 450). Visits during the open-label extension phase will be optional for the female partners.

Number of Subjects:

Double-Blind Phase: It is planned to randomise and treat 250 male subjects for each of the four treatment groups, clinically diagnosed with ED, and their female partners (total N = 1000).

Open-Label Extension Phase: It is planned to include a total of 450 male subjects who have completed the double-blind phase of the study, and their female partners.

Diagnosis and Main Criteria for Admission:

Double-Blind Phase: Male subjects aged 18–70 years with a confirmed clinical diagnosis of ED for more than 3 months (according to the National Institutes of Health Consensus Statement 'the inability to achieve or maintain penile erection sufficient for satisfactory sexual performance at least once'), verified by the IIEF-EF domain (a score of ≤ 25 points at the end of the screening period) and involved in a continuous heterosexual relationship with their partner for at least 6 months.

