9.5 Subject Inclusion and Randomisation

Subjects who sign the ICF for the study at Visit 1 and undergo screening procedures will be identified during screening by a unique screening number. Subjects who fulfil the eligibility criteria will be assigned consecutive subject numbers and randomised before study medication is dispensed on Day 1 of the treatment period (Visit 2).

Subjects will be randomised to receive one of the following gel treatments in a 1:1:1:1 ratio according to a parallel group design (i.e. subjects will receive one treatment only):

- MED2005 0.2% (w/w) GTN gel to deliver a 0.6 mg dose of GTN
- MED2005 0.4% (w/w) GTN gel to deliver a 1.2 mg dose of GTN
- MED2005 0.6% (w/w) GTN gel to deliver a 1.8 mg dose of GTN
- Placebo vehicle

Subjects will be stratified for randomisation based on their baseline ED severity scores from the end of the screening period:

- Mild (IIEF-EF domain score of 17–25)
- Moderate (IIEF-EF domain of 11–16)
- Severe (IIEF-EF domain \leq 10)

It is intended to randomise an approximately equal number of subjects for each baseline severity group. No stratification by site will be done as, with four treatment groups and three baseline ED severity strata, it is not deemed feasible without risking overall balance for treatments.

If a subject discontinues from the study, the subject number will not be re-used and the subject will not be allowed to re-enter the study.

Randomisation will be carried out using an IVRS/IWRS.

For the open-label extension phase, eligible subjects who sign the ICF for the extension phase at Visit 6 will continue in the study. All subjects will receive MED2005 0.6% (w/w) GTN gel to deliver a 1.8 mg dose of GTN.

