14.1 Analysis Sets

The following analysis sets will be used for the statistical analysis of the double-blind phase:

- The **randomised set** will consist of all subjects who were randomised to a treatment
- The **safety set** will consist of all subjects in the randomised set who made use of the medication at least once. In the case of randomisation/treatment errors, subjects will be analysed according to treatment received

- The **full analysis set** (FAS) will consist of all subjects in the randomised set who made use of the medication at least once. In the case of randomisation/treatment errors, subjects will be analysed according to randomised treatment
Primary and secondary analyses will be performed on the FAS.
- The **per protocol set** (PP) will consist of all subjects in the FAS who completed the 12-week treatment period without major protocol violations and who have valid IIEF, SEP Question 2 and SEP Question 3 assessments at Week 12 (Visit 5)

Analysis sets will be identified prior to the unblinding of the study data. The efficacy analysis will be performed as randomised; i.e. a subject will be assigned to the treatment he was initially allocated, irrespective of what treatment was actually applied, and whether or not treatment was discontinued while questionnaire data was collected (see [Section 9.6](#) Withdrawal of Subjects).

In order to assess the consistency of results, sub-group analyses will also be performed according to three subject baseline ED severity groups:

- Mild (IIEF-EF domain score of 17–25)
- Moderate (IIEF-EF domain of 11–16)
- Severe (IIEF-EF domain of ≤ 10)

The following analysis set will be used for the statistical analysis of the open-label extension phase:

- The **open-label analysis set** (OLAS) will consist of all subjects who made use of medication at least once during the open-label extension.

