14.5.3 Primary Analysis

The co-primary efficacy endpoints, assessed in the male subjects, are:

1. The change from baseline of the average of the Week 4, Week 8 and Week 12 IIEF-EF domain scores
2. The change in percentage of sexual intercourse attempts in which subjects were able to insert their penis into their partner's vagina (SEP Question 2) between baseline and the 12 week treatment period
3. The change in percentage of sexual intercourse attempts in which subjects were able to maintain an erection of sufficient duration to have successful intercourse (SEP Question 3) between baseline and the 12 week treatment period

Baseline for the IIEF-EF score is the assessment at Visit 2, baseline for SEP Questions 2 and 3 is the percentage in the screening, treatment free, 4-week period.

The primary objective will be assessed by testing the following hypotheses for each MED2005 dose group (0.6 mg GTN, 1.2 mg GTN or 1.8 mg GTN) and each co-primary endpoint separately, using the FAS:

Null hypothesis (H0): There is no difference in the mean change from baseline in the IIEF-EF domain, SEP Question 2 and SEP Question 3 for the MED2005 treatment group compared with placebo.

$$H0: \mu (\text{MED2005}) = \mu (\text{placebo})$$

Alternative hypothesis (H1): There is a difference in the mean change from baseline in the IIEF-EF domain, SEP Question 2 and SEP Question 3 for the MED2005 treatment group compared with placebo.

$$H1: \mu (\text{active}) \neq \mu (\text{placebo})$$

Each comparison will be carried out at the two-sided 5% level of statistical significance after a Bonferroni correction (p-values multiplied by three). Efficacy will be stated if all null hypotheses for the co-primary endpoints are rejected. However, the three co-primary endpoints will still be considered in a hierarchy of their importance, with the testing order being IIEF-EF domain, SEP Question 3 and SEP Question 2.

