14.5.4 Other Efficacy Variables

All other efficacy variables will be analysed in a supportive way to describe the effect of treatment. Secondary analyses will also be performed on the FAS and with the ANCOVA approach.

Double-blind phase:

The following secondary efficacy analyses will be conducted:

- The analysis of the three co-primary endpoints will be repeated in the three pre-specified subgroups of ED severity: mild, moderate and severe as specified in [Section 14.1](#)
- The change in the IIEF-EF domain, SEP Question 2 and SEP Question 3 at each 4-week visit will be analysed
- Responder analyses assessing the proportion of subjects with a specific increase in the IIEF-EF domain from baseline, using a different responder definition defined separately for each baseline severity group, will be conducted. A responder is defined as having an increase of ≥ 2 , ≥ 5 and ≥ 7 for the mild, moderate and severe subjects, respectively (published Minimal Clinically Important Difference [MCID] according to Rosen *et al.* 2011 [31])
- Responder analyses for SEP Questions 2 and 3 will be conducted in the same way as for the IIEF-EF. A responder is defined as having an increase of -1.3% , 16.7% and 27.3% for SEP Question 2 and 5.0% , 23.3% and 17.0% for SEP Question 3 for patients with mild, moderate and severe baseline ED, respectively (published MCID according to Araujo *et al.* 2012 [32])
- Responder analyses will also be conducted using responder thresholds (that represent meaningful within-patient changes) in the three co-primary endpoints that are determined using a suitable set of data from this study, prior to study unblinding. Receiver operating characteristics (ROC) analyses will be performed to define the thresholds using the PGI-S and PGI-C as anchors, with the thresholds chosen to balance sensitivity and specificity, supplemented with both empirical cumulative distribution functions and probability density functions. The thresholds defined from these analyses will be included in the final SAP prior to breaking the blind.

The following secondary efficacy analyses will be conducted in a more exploratory way making use of the FAS data in the selected doses and placebo over both stages:

- The GAQ will be analysed via logistic regression including terms for treatment group, site and baseline ED severity (categorical variable)

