14.7 Sample Size

A sample size of $n = 250$ per group (total $N = 1000$) provides 90% study power to reject the null hypotheses for all three primary endpoints when comparing a MED2005 dose to placebo, using a Bonferroni corrected type I error, adjusting for three dose versus placebo comparisons. The sample size calculations were performed using EAST 6.4 in the continuous endpoint two-sample multiple comparisons multiple endpoints platform using the assumptions described below.

It is assumed that MED2005 is slightly better than alprostadil [33]. For the higher two doses alprostadil saw an improvement compared to placebo for IIEF-EF of 3.2 and 3.1 (least squares [LS] mean changes), giving an average of 3.15, for SEP Question 2 of 9.6 and 11.3 (LS mean changes), giving an average of 10.65, and for SEP Question 3 of 13.4 and 8.7 (LS mean changes), giving an average of 11.05. In Study FM53 there was a better improvement in SEP Question 3 than SEP Question 2 so the sample size assumptions take this into account. PDE 5's also appear to find SEP Question 2 more difficult to improve compared to placebo than SEP Question 3. Compared with the alprostadil results therefore it is assumed that the difference of MED2005 minus placebo for IIEF-EF is 3.2, for SEP Question 2 is 11.5 and for SEP Question 3 is 12.

Estimates of standard deviations are based on FM53 and published results from other ED treatments and are assumed to be 5.6, 33 and 33 for IIEF-EF, SEP Question 2 and Question 3, respectively [33, 34]. The differences between MED2005 and placebo for each endpoint are assumed to follow a multivariate normal distribution with the following correlation matrix, based on observed data from study FM53.

	IIEF-EF	SEP Question 2	SEP Question 3
IIEF-EF	1	0.5	0.5
SEP Question 2	0.5	1	0.6
SEP Question 3	0.5	0.6	1

For the open-label extension phase it is planned to recruit a total of 450 male subjects in order to meet ICH requirements.

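### Consistency across baseline ED severity is to be assessed by separate stratum analyses, which never compare the strata and, if read by significance, will usually disagree on some endpoint even when the effect is identical

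*Protocol*

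**What the plan says.** Protocol Section 14.1 states the aim: "In order to assess the consistency of results, sub-group analyses will also be performed according to three subject baseline ED severity groups". The groups are mild (IIEF-EF 17–25), moderate (11–16) and severe (10 or below). Section 9.5 stratifies randomisation on them and aims for roughly equal numbers in each.

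Section 14.5.4 and the synopsis state the method: "The analysis of the three co-primary endpoints will be repeated in the three pre-specified subgroups of ED severity: mild, moderate and severe". The analysis to be repeated is the ANCOVA of Section 14.5.3, with treatment, site and continuous baseline. The SEP models also carry severity as a main effect. For IIEF-EF, severity appears only in a sensitivity model. No treatment-by-severity term is stated.

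On significance, Section 14.5.3 says: "Each comparison will be carried out at the two-sided 5% level of statistical significance after a Bonferroni correction (p-values multiplied by three"). Section 14 applies this correction to all p-values from the dose-placebo comparisons and adds matching corrected 95% confidence intervals. The success rule is "Efficacy will be stated if all null hypotheses for the co-primary endpoints are rejected". Section 14.5.4 describes the analyses other than the primary as supportive and descriptive.

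**The concern.** Consistency is a statement about how treatment effects differ between strata. Three separate fits produce three effects and three sets of p-values, but no estimate of any difference between them and no measure of its uncertainty.

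The repeats also split a trial sized for 250 per arm into thirds. The power statement in Section 14.7 covers the whole trial, and none is given for a stratum. A reader who compares significant and non-significant results across strata would therefore see mostly sampling noise. What is at stake is a report that the gel works in one severity group and not in another when the data show no such thing, or a claim of consistency that was never examined.

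**Working it through.** **Inputs (all from the protocol)**
- Arm size: "It is planned to randomise and treat 250 male subjects for each of the four treatment groups" (synopsis). Severity groups are approximately equal (Section 9.5).
- Effects (active minus placebo) for IIEF-EF, SEP Question 2 and SEP Question 3: 3.2, 11.5, 12. SDs: 5.6, 33, 33. Correlations: 0.5 between IIEF-EF and each SEP question, 0.6 between the SEP questions (Section 14.7).
- Two-sided alpha per comparison 0.05/3 = 0.0167, so z = 2.394 (Section 14.5.3).

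**Formulas.** SE = SD × √(2/n). Power for one endpoint = Φ(effect/SE − 2.394). Joint power is the trivariate normal probability, with the stated correlations, that all three statistics exceed 2.394.

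**Step 1: reproduce the plan's figure.** Section 14.7 says that 250 per arm "provides 90% study power to reject the null hypotheses for all three primary endpoints when comparing a MED2005 dose to placebo". At n = 250 the marginal powers are above 99.9%, 93.4% and 95.3%, and joint power is 90.4%. The stated figure is reproduced.

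**Step 2: one stratum.** n = 250/3 = 83.3 per arm, so √(2/n) = 0.1549. The same effect and SD are assumed in every stratum.

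| Endpoint | SE | effect/SE | Power |
|---|---|---|---|
| IIEF-EF | 5.6 × 0.1549 = 0.868 | 3.69 | 90.2% |
| SEP Question 2 | 33 × 0.1549 = 5.11 | 2.25 | 44.3% |
| SEP Question 3 | 33 × 0.1549 = 5.11 | 2.35 | 48.1% |
| All three jointly | | | 31.0% |

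**Step 3: pattern across strata under the three-endpoint rule.** The strata are independent.
- All three succeed: 0.310³ = 3.0%.
- None succeeds: 0.690³ = 32.9%.
- One or two succeed: 100 − 3.0 − 32.9 = 64.1%.

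Among simulated trials in which the dose wins overall, all three strata succeed in 3.3% and none does in 26.9%.

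**Step 4: pattern endpoint by endpoint.**
- Significant in all three strata (power cubed): IIEF-EF 73.5%, SEP Question 2 8.7%, SEP Question 3 11.2%.
- Significant in some strata but not others: about 26%, 74% and 75% respectively.
- At least one endpoint mixed in this way: 93% (300,000 simulated trials, one dose). At an unadjusted 0.05 it is 87%.
- All nine estimates (three endpoints by three strata) favour active: 94% (same simulation).

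**Step 5: precision of a direct comparison.** The SE of a difference between two stratum effects is √2 times the stratum SE: 1.227 for IIEF-EF and 7.23 for SEP.
- 95% half-width: 1.96 × 1.227 = 2.4 IIEF-EF points; 1.96 × 7.23 = 14 SEP points.
- Bonferroni half-width: 2.394 × 1.227 = 2.9; 2.394 × 7.23 = 17.
- Suppose the effect is absent in one stratum and as planned in the other two. A 2-df heterogeneity test at 0.05 for one dose then has power of 77% (IIEF-EF), 36% (SEP Question 2) and 39% (SEP Question 3).

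**The case against.** The strongest reply is that the protocol never says consistency will be judged by which strata reach significance. The success rule in Section 14.5.3 serves the primary objective on the whole FAS. Repeating the primary analysis also yields treatment differences (Section 14.5.3) and corrected confidence intervals (Section 14), so stratum estimates with intervals are already planned. Read by direction of effect, the strata would agree in about 94% of trials. On IIEF-EF, ranked first, all three would be significant in about 73.5%. This stands. The probabilities above hold for a reading by significance, which the protocol invites by labelling every comparison but does not prescribe.

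A second reply is that an interaction test is detail for the SAP. This stands in part. A SAP may add one, and its absence alone would be no finding. The point is narrower: the protocol names a question and a method, and that method does not compare the strata.

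Third, the replacement is itself imprecise. That also stands. The 95% half-width of 14 SEP points exceeds the planned SEP effects of 11.5 and 12.

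Fourth, Section 14.5.4 sets responder thresholds that differ by severity, so an equal raw-scale effect need not mean equal benefit. That bears on interpretation. It does not make separate fits a comparison.

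**Conclusion.** The point holds in a limited form. The stated method cannot answer the stated question. If it is read by significance, an identical effect gives the same three-endpoint success in every stratum in about 3% of trials, and a mixed result on at least one endpoint in about 93%. The shortfall comes from SEP Questions 2 and 3.

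A reader might infer that a homogeneous effect would almost surely be reported as present in some severity groups and absent in others. The 3% figure does not show that. Under the three-endpoint rule the pattern is mixed in about 64% of trials, and in about 33% no stratum succeeds, which is a uniform verdict. Nor does anything here weaken the primary conclusion: the analysis is supportive and no subgroup claim is planned.

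The figures assume equal thirds, the overall SD within each stratum, no dropout and no loss from the site terms.
- With SDs at 0.8 to 1.1 times the stated values, all three strata succeed in 16.7% to 1.3% of trials.
- A stratum holding 20% of subjects (50 per arm) has 13.9% joint power.
- Fitting about 50 site terms to about 333 men would multiply the variance by about 1.17 if site explains no outcome variance. Joint power per stratum then falls to about 24.5%.

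**What to change.** In the full-FAS ANCOVA for each co-primary endpoint, add a treatment-by-baseline-severity interaction. The SEP models already contain the severity main effect. The IIEF-EF model needs that main effect as well, as in the planned sensitivity analysis. Report the treatment effect in each stratum, with its confidence interval, from that one model. State in Sections 14.1 and 14.5.4 that consistency is read from these estimates and from the interaction, not from stratum p-values.

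The cost is one added analysis per endpoint and no new data. The interaction has (4 − 1) × (3 − 1) = 6 degrees of freedom over the four arms, or 2 for a single dose against placebo. The single model assumes common site effects, baseline slope and residual variance across strata. Its main drawback is imprecision: between-stratum differences are known only to about ±2.4 IIEF-EF or ±14 SEP points at 95%, and ±2.9 or ±17 at the Bonferroni level. The text should therefore add that a non-significant interaction is not proof of consistency.

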14.2 Demographic and Baseline Measurements

Assessments made at screening and at baseline of the treatment period will be summarised overall and for each treatment group. These assessments will include demographic and other relevant baseline characteristics (such as medical history, physical examination and the assessments made during the screening period). There will be no formal comparison of baseline data; that is, no statistical hypothesis testing.

14.3 Prior and Concomitant Medication

Prior and concomitant medication will be summarised overall and by treatment. For further information, please also refer to [Section 10.5](#).

14.4 Number of Intercourse Attempts

Use of study medication and number of intercourse attempts will be summarised by treatment and 4-week period. Mean and median number of intercourse attempts will be given as well as an absolute and relative number of subjects tabulated by number of intercourse attempts.

14.5 Efficacy Evaluation

14.5.1 Efficacy Measures

For a list of efficacy assessments, see [Section 11.2](#).

Summary statistics for all efficacy measures will be given by treatment, 4-week period (double-blind phase) and 3-month period (open-label extension phase) and gender (where applicable), for actual values and changes from baseline. Individual components of composite scores (but not domains) will not be summarised unless otherwise stated. Individual components as well as domains will be presented in listings together with the scores used in the analysis.

The co-primary efficacy outcomes will be change from baseline to 12 weeks of treatment in the IIEF-EF domain, SEP Question 2 and SEP Question 3 at Week 12.

Listings and summary statistics for the IIEF-EF, SEP Question 2 and SEP Question 3 will also be provided for the subsets in the open-label extension phase of the study.

14.5.2 Handling of Missing Values

Full details on the handling of missing values in analyses of all analysis sets, including rules applied to incomplete questionnaires and planned additional analyses, will be defined in the SAP. Only the main principles are given for the analyses on the FAS here.

Summary statistics will present the number of missing values and then will be based on non-missing values.

Any missing values in efficacy questionnaire data that occur during the treatment period and are then followed by observed data shall be treated as missing at random and imputed using a corresponding multiple imputation approach.

All subjects who are withdrawn from the study will be asked to continue with the IIEF and SEP questionnaires if possible. These data will be used as part of the analysis for estimating the treatment effect over 12 weeks, according to the randomised treatment policy.

There can be remaining missing values for the primary endpoints for subjects who leave the study and provide no further questionnaire data. For these subjects, missing values will be handled using a control-based multiple imputation approach. The imputation model for the missing observations in both the MED2005 and placebo (control) groups will be constructed from the control group only (missing not at random [MNAR]). This assumes that efficacy results post withdrawal, for subjects who withdraw, would have mirrored those seen in the placebo group and thus lose any potential MED2005 treatment benefit.

Additional estimands/tests of treatment effect, beyond the primary treatment policy estimand, may be addressed, including exploring other ways of handling missing values, such as fitting repeated measures mixed models.

Summary statistics will present the number of observed values and will then be based on the non-missing values for the open-label extension phase.

